Pilot Study of Natriuretic Versus Standard Doses of Mineralocorticoid Receptor Antagonists in
Heart Failure and Loop Diuretic Resistance in Outpatients

NCT: 02585843

Date 8/30/2015

Study Design

We conducted a pilot, prospective, single-center, double-blind, randomized, placebo controlled trial assessing the effects of high dose spironolactone in addition to intensified loop diuretic therapy vs. standard medical therapy in outpatients with ADHF. Our primary outcome was defined as weight change over the seven day study period. Based on data from a non-randomized intervention study, we aimed to recruit a total sample size of 40 subjects to detect a difference in our primary outcome of weight loss of 1.5kg difference between treatment and control.

On Day 1, all potential subjects were evaluated with complete medical history and physical examination, review of home medications, measurement of vital signs and body weight with a calibrated scale, serum collection for basic metabolic panel, liver function test, biomarkers of congestion, and electrocardiogram. "Imminent hospitalization" was determined by two independent HF specialists to assess the need for hospitalization for intravenous diuretics. Home MRAs were discontinued and potassium supplementation held if baseline serum potassium was >4.0mmol/L. Beta-blockers, ACE-I or angiotensin II receptor blockers were continued at home dose. Loop diuretic dosage was increased by two-fold. Patients were seen at two office visits in total, baseline at day 1 and final visit on day 7. On day 3, participants had serum basic metabolic panel to assess potassium levels and renal function for safety assessment.

Intervention

Enrolled patients were randomly assigned in a 1:1 ratio to high-dose (100mg/day) or standard-dose (25mg/day) spironolactone treatment groups.

Randomization, Allocation and Blinding

Randomization was stratified by sex and EF<45% in blocks of size 4. 2 by 2 randomization was performed via computer model generated by a study investigator. Allocations were concealed via the locked research pharmacy and the research team was blinded to treatment arm. All treatment medications were labeled in a blinded fashion. Subjects received 2 capsules per day (if standard dose: 25mg and placebo, if high dose: two 50mg) dispensed in vials of 2 capsules.

Study Endpoints

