Pilot Study of Natriuretic Versus Standard Doses of Mineralocorticoid Receptor Antagonists in
Heart Failure and Loop Diuretic Resistance in Outpatients

NCT: 02585843

Date 8/30/2015

Study Endpoints

The primary endpoint for the study was defined as change in total body weight at day 7 of the study period. Multiple secondary endpoints from day 1 to 7 were assessed. These included a) changes in dyspnea assessment scores; Visual Analogue Scale and 7-Likert scale, b) signs of congestion (i.e. JVP, peripheral edema and respiratory rales), c) 6MWT, d) serum and urinary creatinine, sodium, potassium and plasma aldosterone and renin activity and biomarkers of congestion and neurohormonal activation, e) furosemide equivalent of treatment loop diuretics doses, e) hospitalization at 30-, 60- and 90-days.

Six-minute walk test was performed per American Thoracic Society guidelines, along with Borg scores for dyspnea and fatigue at day 1 and 7. Serum and urinary creatinine, potassium, and sodium, plasma aldosterone and renin activity, and pro-BNP were assessed at days 1 and 7. Other biomarkers of peripheral congestion (CD146), inflammation (interleukin-6, tumor necrosis factor- α , endothelin-1) oxidative stress (isoprostane) and endothelial activation (vascular cell adhesion molecule-1) were assessed at day 1 and 7 and analyzed by ELISA or LC-MS.

A data monitoring committee of two independent cardiologists was established to evaluate safety, with a pre-specified stopping rule for harm but not for efficacy. Safety endpoints included changes in serum creatinine levels, eGFR, and the incidence of hyperkalemia during the 7 day treatment period. Safety was assessed by tracking adverse events including new or worsening renal dysfunction, and hyperkalemia. Serious adverse events were defined as death and all-cause hospitalization.

Statistical Analysis

Statistical analyses were performed using SPSS version 23. Continuous variables are presented as mean \pm SD (or median with IQR if not following normal distribution) and categorical variables were summarized as counts (percentages). The χ^2 test or Fisher's exact test (when cell counts were small) were used to compare categorical variables. Paired t-tests and the Wilcoxon rank sum test was used to compare continuous variables pre vs. post intervention within treatment arms. ANOVA was performed to compare continuous variables post-intervention. P< 0.05 considered statistically significant for all comparisons.

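### The SAP ties no between-arm test to the 7-day weight change on which the trial is sized, and gives within-arm tests the same P<0.05 status

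*SAP*

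**What the plan says.** The endpoint is single and clear. In the SAP, Study Endpoints: "The primary endpoint for the study was defined as change in total body weight at day 7". The protocol, Study Design, sets a total of 40 subjects to "detect a difference in our primary outcome of weight loss of 1.5kg difference between treatment and control". The question is therefore a comparison of change between arms.

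The SAP, Statistical Analysis, gives three generic rules and does not assign any of them to the primary endpoint:

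- Categorical variables: chi-square or Fisher's exact test. These do not fit a weight change in kg.
- Continuous variables, over time: paired t-tests and a Wilcoxon test to "compare continuous variables pre vs. post intervention within treatment arms".
- Continuous variables, afterwards: "ANOVA was performed to compare continuous variables post-intervention".

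The section closes with one threshold: "P< 0.05 considered statistically significant for all comparisons".

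On treatment, the protocol's Intervention section assigns patients to "high-dose (100mg/day) or standard-dose (25mg/day) spironolactone treatment groups". Its Study Design section says, without restriction by arm, "Loop diuretic dosage was increased by two-fold".

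**The concern.** The design and the analysis section do not meet. The design asks whether weight change differs between arms. The only rule in the SAP that plainly analyses a change works inside one arm at a time. The rule that could compare arms mentions neither arms, nor change, nor weight.

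Two things are at stake. First, the choice between analysing change and analysing the day-7 value decides whether a trial of this size can detect 1.5 kg at all, and the text leaves that choice open. Second, weight is a continuous variable measured before and after treatment, so it falls under the paired tests too, and those carry the same significance rule. Both arms receive active diuretic treatment, so weight can fall in both without any dose effect. If the fall is significant at 100 mg/day and not at 25 mg/day, the SAP allows the first result to be reported as significant even when the randomized comparison is not.

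**Working it through.** **Inputs.** From the documents: total of 40, 1:1 allocation (20 per arm), difference 1.5 kg, P<0.05. Not stated: SD, power, sidedness, dropout, expected loss in the standard-dose arm. Assumed: two-sided tests, no dropout, normal changes, the same SD in both arms.

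**1. Which SD fits the plan's N of 40?** N cannot be reproduced directly without an SD and a power, so the SD is back-solved. For a two-sample t-test with n = 20 per arm (38 df, critical value 2.024), the noncentrality is d·√(n/2) = 3.162·d, where d = 1.5/SD.

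- 80% power needs d = 0.909, so SD = 1.5/0.909 = 1.65 kg.
- 90% power needs d = 1.052, so SD = 1.5/1.052 = 1.43 kg.

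N = 40 is thus consistent with a between-arm test of *change* at an SD of about 1.4–1.65 kg.

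**2. The ANOVA read literally, on day-7 weight.** The noncentrality is 1.5/(SD·√(2/20)), with SD now the between-subject SD of body weight. The documents give none; 10–25 kg is assumed.

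| SD of weight (kg) | Noncentrality | Power for 1.5 kg |
|---|---|---|
| 10 | 0.474 | 7.5% |
| 15 | 0.316 | 6.1% |
| 20 | 0.237 | 5.6% |
| 25 | 0.190 | 5.4% |

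This is barely above the 5% error rate.

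**3. Within-arm tests when there is no dose effect.** Let both arms have the same true mean loss m. In each arm the paired t-test has 19 df, critical value 2.093 and noncentrality m/(SD/√20). Let p be its probability of P<0.05. The arms are independent, so the chance that only the high-dose arm is significant is p(1−p). For example, at m = 1 kg and SD 1.65 the noncentrality is 2.71, p = 0.730, and 0.730 × 0.270 = 0.197.

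| SD of change (kg) | p at 0.5 / 1 / 1.5 kg | High-dose arm only, at 0.5 / 1 / 1.5 kg |
|---|---|---|
| 1.43 | 0.318 / 0.843 / 0.993 | 21.7% / 13.2% / 0.6% |
| 1.65 | 0.251 / 0.730 / 0.971 | 18.8% / 19.7% / 2.8% |
| 2 (assumed) | 0.186 / 0.565 / 0.889 | 15.1% / 24.6% / 9.9% |
| 3 (assumed) | 0.109 / 0.294 / 0.565 | 9.7% / 20.7% / 24.6% |

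At 2 kg loss the chance is below 0.1% for the two back-solved SDs and about 16% for an SD of 3 kg. The p values are power to detect a real fall in weight, not error rates.

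**4. The same pattern with a non-significant between-arm test.** Simulation of 200,000 trials per cell gives 0.195 / 0.115 / 0.004 at 0.5 / 1 / 1.5 kg for SD 1.43, and 0.167 / 0.177 / 0.022 for SD 1.65. The between-arm t-test of change rejects in 4.9–5.1% of these trials, as it should.

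**The case against.** **The between-arm test can be inferred.** The sample size is stated between treatment and control, the endpoint is defined as a change, and the SAP sets within-arm tests against an ANOVA. By elimination the ANOVA is the between-arm test, and an ANOVA of the primary endpoint is an ANOVA of change. This is probably what was meant. It makes raw day-7 weight the less plausible reading, and the weight SD used for it is an assumption. But the text says neither between arms nor change; the one word it does use points to values after treatment.

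**The within-arm harm is conditional.** Where both arms truly lose weight, a significant within-arm test is a correct finding. Reporting pre/post changes is ordinary practice. The error arises only if someone infers a dose effect from it. That stands. A reader might infer that the SAP intends to claim efficacy from within-arm tests; it does not say so, though it does not rule it out.

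**The size depends on the common loss.** At the back-solved SDs the risk is concentrated at modest losses and almost vanishes by 2 kg. With a doubled loop diuretic, larger losses are plausible, and the documents give no expected value. That also stands.

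**The multiplicity reading.** A reader might infer from one unadjusted threshold, together with "Multiple secondary endpoints from day 1 to 7 were assessed", that the trial's error rate is uncontrolled. The documents do not support that. They name one primary endpoint, call the others secondary, and describe a pilot. A single between-arm test of the primary endpoint keeps its 5% level, and unadjusted secondary endpoints are usual in a pilot.

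**Conclusion.** The point holds as a specification gap with consequences. No stated figure is shown to be wrong, and N = 40 is consistent with a between-arm test of change. But the rules as written do not deliver the comparison for which the trial was sized.

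Two sizes attach to it. The literal ANOVA on day-7 weight would leave about 5–8% power, against the 80–90% from which the SD of change was back-solved; this rests on an assumed weight SD of 10–25 kg. A high-dose-only significant result would arise by chance in roughly one trial in five to one in eight at common losses of 0.5–1 kg, and rarely at 1.5 kg or more unless the SD exceeds the back-solved range. This rests on assumed power, equal SDs and no dropout.

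The argument also reads the loop-diuretic doubling as applying to both arms, as the sentence stands. Even without it, both arms receive spironolactone, so a change inside one arm would not isolate the dose.

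The SAP should be changed, but the case is moderate: the intended test can be guessed, and the within-arm risk needs a misreading to do harm.

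**What to change.** Add to the SAP, Statistical Analysis, wording such as:

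*The primary analysis is the between-arm comparison of change in body weight from day 1 to day 7, by one-way ANOVA of change (with two arms, equal to the two-sample t-test), at two-sided P<0.05, reported as the mean difference with its 95% CI. It is the only basis for a claim of effect on the primary endpoint. Within-arm changes are reported descriptively with 95% CIs and are not used to infer a dose effect.*

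This keeps the SAP's own method. An ANCOVA with baseline weight and the stratification factors would be a reasonable alternative, but nothing in the documents requires it. Labelling secondary endpoints exploratory is optional.

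The cost is wording only, with no new data or subjects. The downside is that fewer results can be called significant, although every estimate is still reported. Both documents are written in the past tense, so the change should be dated and should say whether outcome data had been seen. If they had, it clarifies the analysis but does not restore pre-specification.
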